All patients who receive a dose of pembrolizumab and trametinib will be analyzed for safety and efficacy. Subjects who discontinue from study participation prior to receiving the combination of trametinib and pembrolizumab will be replaced. Subjects in dose escalation who discontinue from study and are not evaluable for dose limiting toxicities will be replaced. Patients removed from study for unacceptable treatment related adverse event(s) will be followed until resolution or stabilization of all treatment related AEs to grade 2 or lower. However, they will not be replaced.

A group of 12 patients will be enrolled in each of the 2 expansion cohorts at the MTD. Patients will enroll into the next subsequent cohort upon completion of the previous cohort (Arm A then Arm B). A sequencing scheme will be considered as promising if at least 5 of 12 patients were to achieve a complete or partial response per RECIST 1.1. The decision rule is associated with 80% exact power with an exact alpha of 0.16 if the underlying response rate associated with a sequencing scheme were truly at least 50% compared to current expectation of 25% ORR with single agent pembrolizumab. A median PFS of 8 months in 12 patients per cohort will provide 81 power to detect a difference compared to historical PFS of about 4 months with single agent pembrolizumab with an alpha of 0.1 based on accrual time of 24 months and follow up of 12 months. A sequencing scheme will be recommended for further development based on a combination of promising efficacy (response rate, PFS) and favorable changes in the tumor immune microenvironment at rebiopsy, provided the safety and tolerability profiles are acceptable.

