All molecular and immune correlates will be assessed in exploratory analyses. Due to the limited sample size and exploratory framework, any such analysis will be stated carefully as hypothesisgenerating with the reported p-values not adjusted for multiple comparisons. Standard descriptive and graphical methods will be used to summarize the baseline levels and post-treatment changes for comparison of the three MEKi and pembrolizumab sequencing schemes, which will allow us to examine whether observed patterns are consistent with hypothesized mechanisms. The quantitative immune studies will be compared using a t-test to further inform the decision. Multiplicity of testing will not be considered since this considered an exploratory analysis. Association with response rate will be summarized descriptively by presenting the mean, SD, and other characteristics of molecular and immune measures, stratified by response status. Associations of molecular and immune measures with PFS will be summarized descriptively by stratified Kaplan-Meier curves and, if numbers permit, by proportional hazards models with molecular and immune responses as predictors. If the MEKi and pembrolizumab combination were not found to have sufficient activity, the molecular and immune patterns may

help explain the lack of activity. If sufficient activity were observed, then the correlates will be compared between patients who experience an objective response and those who did not. Results of these correlative studies including biopsies at pre-treatment and week 1 on treatment will be analyzed in conjunction with the Battle-Immunotherapy trial (with its later biopsy correlative timepoints) to inform the optimal dosing and sequencing of pembrolizumab with trametinib.

Decisions for whether to pursue one of these strategies in a larger trial will incorporate ORR, toxicity and immune correlative endpoints in collaboration with the company sponsors and SU2C Dream Team. The primary considerations will be ORR and toxicity, with immune and genomic correlative studies used as supplementary criteria.

If only one arm meets safety criteria and preliminary efficacy criteria (ORR \geq 50% or a median PFS \geq 8 months), then that treatment will be considered for future study. Immune and genomic correlative studies will be examined for the potential to inform future study design for that arm.

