If both arms A and B meet the safety criteria and preliminary efficacy criteria and give comparable response rates and toxicities, we will carry out two additional sets of analyses to inform the decision process of which treatment to pursue for further study. First, we will use regression models to assess whether one arm might have superior performance after accounting for key patient differences (PD-L1 status, KRAS amino acid substitution (G12C vs. non-G12C), smoking status). We will assess whether one arm has superior ORR, using logistic regression analysis to control for clinical covariates, and whether one arm has superior PFS, using proportional hazards models to control for clinical covariates. Second we Second, we will examine biomarkers that might shed light on the impact of the treatments. We will compare exploratory immune correlates (enhanced tumor immune microenvironment). The final decision will be based on best clinical judgment of all investigators.

We expect that the distribution of PD-L1 expression in Arm A and Arm B to be comparable. Based on the current indication for first line pembrolizumab in PD-L1 high (>50%) NSCLC, the majority of patients accrued into this second line trial will likely contain tumors with lower PD-L1 expression. At completion of Arm A we will review baseline characteristics and current clinical practice at that time to assess whether it is anticipated there would be a shift in biomarker distribution in Arm B.

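### The t-test for the immune measures states neither the quantity tested nor any baseline covariate; a baseline-adjusted comparison would suit these sequential, non-randomised arms better (minor)

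*Combined protocol and SAP*

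**What the plan says.** The test is given in one sentence of section 8.0: "The quantitative immune studies will be compared using a t-test to further inform the decision". The plan does not say whether it is paired or two-sample, whether it is applied to on-treatment values or to changes, or whether any covariate enters. The sentence before it promises descriptive and graphical methods to "summarize the baseline levels and post-treatment changes for comparison of the three MEKi and pembrolizumab sequencing schemes". That wording counts three schemes, although the trial has two arms.

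The weight of the analysis is stated openly. "All molecular and immune correlates will be assessed in exploratory analyses", p-values are not adjusted for multiplicity, and for the choice of strategy "The primary considerations will be ORR and toxicity, with immune and genomic correlative studies used as supplementary criteria". If both arms qualify with comparable response and toxicity, section 8.0 adds two analyses. ORR and PFS get regression models with patient covariates. The immune correlates are simply to be compared.

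On design, "A group of 12 patients will be enrolled in each of the 2 expansion cohorts at the MTD", with Arm A filled before Arm B. At the end of Arm A the team will review baseline characteristics and clinical practice to "assess whether it is anticipated there would be a shift in biomarker distribution in Arm B".

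On sampling, section 8.0 lists immune studies in baseline and repeat biopsies, and footnote 10 of the Study Calendar schedules immune blood before cycle 1. Inclusion criterion 7 allows an archived baseline specimen under conditions. The processing instructions in section 7.1.2.7 warn that sparse samples may not support PD-L1 staining.

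**The concern.** A comparison between two small, consecutively filled groups is exposed to baseline differences from chance and from calendar time. The plan recognises the second risk when it schedules a review for a biomarker shift, but gives no analysis that would deal with one. It adjusts ORR and PFS for patient differences and leaves the immune measures out, although these have the most natural covariate available: the same measure before treatment.

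The immune result would carry most weight when response and toxicity do not separate the arms. A difference that only reflects who was enrolled in which period could then tip the choice of sequence.

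**Working it through.** **1. The plan's own figure for 12 per arm.** The documents give no power, SD or effect size for the immune test. The 12 comes from the response rule (at least 5 of 12, 25% against 50%). Exact binomial: P(X ≥ 5 | 12, 0.25) = 0.158 and P(X ≥ 5 | 12, 0.50) = 0.806. The stated alpha of 0.16 and power of 80% reproduce.

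**2. Inputs for the immune comparison.** From the documents: 12 per arm, two arms, N = 24. Section 2.1 places the microenvironment comparison in the expansion cohorts. Assumed, because the documents give none: two-sided 0.05, normal values with equal variances, baseline/on-treatment correlation ρ from 0 to 0.9, baseline shift of 0 to 1 SD, and true effect of 0 or 1 SD.

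**3. Bias from a baseline shift.** If the on-treatment value depends linearly on baseline with slope ρ, the arms differ at baseline by s SD, and there is no true effect, then:

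- t-test on on-treatment values: bias = ρs
- t-test on changes: bias = (ρ − 1)s
- model with baseline as covariate (ANCOVA): bias = 0 under this model

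With s = 1 and ρ = 0.5 these are +0.50, −0.50 and 0 SD. The two t-tests err in opposite directions. False-positive rates from simulation (40,000 trials per setting, 12 per arm):

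| Shift (SD) | ρ | Values | Changes | ANCOVA |
|---|---|---|---|---|
| 0.5 | 0.5 | 9% | 9% | 5% |
| 1 | 0.5 | 22% | 21% | 5% |
| 1 | 0.7 | 37% | 15% | 5% |

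At ρ = 0.5 the two t-tests have the same variance and equal and opposite bias, so the gap between 22% and 21% is simulation noise.

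**4. Precision without a shift.** Variance relative to a t-test on values is 2(1 − ρ) for changes and (1 − ρ²)(N − 3)/(N − 4) for ANCOVA. At ρ = 0.5 and N = 24 these are 1.00 and 0.75 × 21/20 = 0.7875. The ANCOVA standard error ratio is √0.7875 = 0.887, about 11% smaller. At ρ = 0 it is √1.05 = 1.025, or 2.5% larger.

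Power for a true difference of 1 SD, simulated:

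| ρ | Values | Changes | ANCOVA |
|---|---|---|---|
| 0 | 65% | 38% | 63% |
| 0.3 | 65% | 51% | 67% |
| 0.5 | 65% | 65% | 75% |
| 0.7 | 65% | 86% | 89% |

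**5. Where adjustment stops paying.** Against a t-test on values, the variances are equal when (1 − ρ²) × 21/20 = 1, so ρ = √(1/21) = 0.22 (0.23 when the lost degree of freedom in the t quantile is counted). Counted that way, break-even is 0.28 with 9 evaluable pairs per arm and 0.37 with 6. Against a t-test on changes, ANCOVA is more precise when 1.05(1 + ρ) < 2, that is ρ < 0.90.

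**6. Standard error under a shift.** Adjustment removes the bias but can cost precision. With a 1 SD shift the ANCOVA standard error is 0.413 against 0.407 for values at ρ = 0.5, and 0.465 against 0.411 at ρ = 0.2.

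**The case against.** The strongest reply is that the plan may already use baseline. The preceding sentence speaks of changes after treatment, and the recommendation criterion in section 8.0 is favourable change at rebiopsy, so a t-test on changes is a natural reading. A reader might infer from the bare t-test that baseline is ignored altogether; the text does not establish that. But the change reading does not remove the problem, because a change score over-corrects for a baseline shift whenever ρ is below 1 (step 3). Its loss of power is large at low ρ and small at 0.7.

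Two further inferences also go too far. One is that every patient will have a usable baseline. Collection is planned for all, but tissue may be archival or too sparse for PD-L1, and a complete-case adjusted model would drop patients whom a t-test on values would keep. The other is that adjustment is always more precise and free. Steps 5 and 6 show when it is not.

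It is also fair to say that these measures are skewed and bounded whereas the calculations use normal data, and that in non-randomised arms freedom from bias rests on the linear model being right. Adjusting for baseline does not deal with other differences between enrolment periods. Finally, the analysis is labelled exploratory, no decision threshold attaches to the t-test, and the final choice rests on clinical judgment. All of this stands, and it limits the importance of the point without making the t-test the better choice.

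**Conclusion.** The concern holds as a minor, inexpensive improvement. The plan does not define what the t-test compares and names no baseline covariate, in a setting where baseline samples are planned and the arms are neither concurrent nor randomised. With a 1 SD baseline shift at ρ = 0.5, either form of t-test has a false-positive rate about four times the nominal 5%; with a 0.5 SD shift it is about 9%. With no shift, the gain in power over a t-test on values is about 10 points at ρ = 0.5, 2 points at 0.3, and a loss of about 2 points at 0. These sizes depend on assumed values of ρ, shift and effect, normal data, linearity and 12 complete pairs per arm. The documents do not show that a shift will occur; they only foresee checking for one. Nothing here touches the response rule, the sample size or the primary objective.

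**What to change.** In section 8.0, replace the t-test sentence with the following:

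- **Model.** The exploratory between-arm comparison is a linear model of the on-treatment value on arm and the baseline value of the same measure, with the time point named for each measure. Report the adjusted difference with a confidence interval.
- **Scale.** State a transformation that allows zeros, for example a log with a stated offset. For bounded PD-L1 percentages add a rank-based version as a sensitivity analysis, since ranks do not give a difference on the measurement scale.
- **Missing or archival baselines.** State the rule, for example also reporting the unadjusted comparison in all patients with an on-treatment value, and flagging archival baselines.
- **Wording.** Bring the reference to three schemes into line with the two arms, and keep the exploratory label.

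The cost is SAP wording and one degree of freedom. The downsides are a slight loss of precision if the correlation is below about 0.22 (higher with fewer evaluable pairs), loss of patients without a usable baseline from the adjusted analysis, and reliance on the linear model. No change to design, sample size or data collection is needed.

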5.2 Trial Treatments

The treatment to be used in this trial is outlined below in Table 2.

Table 2. Trial Treatments

Drug	Dose/Potency	Dose Frequency	Route of Administration	Regimen/Treatment Period	Use
Pembrolizumab (MK-3475)	200 mg	Q3W	IV infusion	Day 1 of each 3 week cycle	Experimental
Trametinib	x mg†	Daily†	PO	Daily starting D1	Experimental
† See dose escalation schema. RP2D for expansion cohorts.					

Dose Escalation Cohort (Arm A): Trametinib will be adminstered starting C1D1 and continued as per Table 3, until determination of the MTD. Pembrolizumab will be added to trametinib starting C2D1.

Dose Escalation Cohort (Arm B): Pembrolizumab will be administered starting C1D1 and trametinib will be added to pembrolizumab starting C2D1.

Expansion Cohort (Arm) A: Trametinib will be administered starting C1D1 and pembrolizumab will be added to trametinib starting C2D1 at the MTD of the combination as determined from the dose escalation portion of the study.

Expansion Cohort (Arm) B: Pembrolizumab will be administered starting C1D1 and trametinib will be added to pembrolizumab starting C2D1 at the MTD of the combination as determined from the dose escalation portion of the study.

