- 7. The initial tumor imaging will be performed within 30 days prior to the first dose of trial treatment. Scans performed as part of routine clinical management are acceptable for use as the screening scan if they are of diagnostic quality and performed within 30 days prior to the first dose of trial treatment. On-study imaging will be performed every 9 weeks (63 ±7 days) after the first dose of trial treatment or more frequently if clinically indicated. The timing for imaging studies should follow calendar days and should not be adjusted for delays in cycle starts or extension of pembrolizumab /trametinib cycle frequencies. The same imaging technique should be used in a subject throughout the trial. CT including the chest, abdomen and pelvis or PET-CT is required for the baseline assessment. Patients who discontinue for reasons other than progression will be followed by imaging every 9 weeks.
- 8. Pembrolizumab (MK-3475) can be administered for up to 2 years. For the dose escalation and expansion Cohort (Arm) A (concurrent trametinib and pembrolizumab (MK-3475) both drugs will be administered as outlined in this protocol starting with cycle #1. For cohort B. trametinib will be initiated with cycle #1 and pembrolizumab (MK-3475) will commence in combination with trametinib starting with cycle #2, for Cohort C pembrolizumab (MK-3475) will be given for cycle 1 with concurrent trametinib added on C2D1.
- 9. Tumor biopsy for immune and molecular biomarker analysis will be performed prior to Cycle 1 of treatment either on archival tissue or fresh biopsy (within 6 months—no intervening treatment). Repeat biopsy will be performed on cycle 1 D11-13 or within 2 days after the last dose of trametinib for Arm A) and an optional end of study biopsy (within 28 days after progression).
- 10.Correlative blood draws for immune correlates will be performed prior to cycle 1 (- 3 days), prior to cycle 4 (-3 days), prior to cycle 7 (-3 days) and at discontinuation visit (± 5 days). Correlative blood draws for plasma DNA/RNA will be performed at baseline (cycle 1, day 1 prior to dosing or prior during screening), prior to each cycle of treatment (prior to concurrent administration of trametinib and pembrolizumab), and at progression (± 5 days).
- 11. Ophthalmology Exam: Indirect fundoscopic examination, visual acuity (corrected), visual field examination, tonometry, and direct fundoscopy within 6 weeks prior to registration.

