The tubes should be centrifuged as soon as possible at approximately 800 x g for 10 minutes. Plasma should be transferred to a 15 mL conical tube and centrifuged a second time at 1000 – 1500 x g for 10 minutes. After the second centrifugation, aliquot plasma in 500 ul aliquots into labeled cryovials. For peripheral blood mononuclear cell (PBMC) preparation, replace the plasma removed with an equal amount of PBS (Ca and Mg free) in the original lavender-top tubes, and then slowly layer it on top of the 15ml of Ficoll in a 50ml conical tube, followed by centrifugation at 800 x g for 20 minutes with the break off. The buffy coat, a whitish layer of cells between the PBS and Ficoll layers above the red blood cell layer, should be collected and transferred into a new 50ml tube, washed once with 50ml of PBS, re-suspended in an appropriate volume of freezing medium and then transferred into labeled cryovials (10⁷/ml/vial). All cryovials are then to be frozen as rapidly as possible, and stored in a -70 degree freezer until batch analysis is feasible by the HIMC.

Molecular correlates tissue – whole exome sequencing, determination of mutational load and RNA sequencing will be performed by the Broad Institute as part of the SU2C Team. A tube of blood will be collected for germline DNA comparison. Kits will be provided by the Broad Institute.

Immune Studies Tissue

Tumor biopsy at three time points with a biopsy prior to treatment, cycle 1, day 11 (+/- 2 days) and within 28 days post-treatment upon progression for immune correlates (optional), anti-apoptotic proteins, p-ERK by multiplexed immunofluorescence. Next generation sequencing on baseline and post-progression biopsies will also be conducted by the Broad Institute, conducted by the Stand Up to Cancer Core Facility, the Broad institution (NGS), the [name] lab and Theranostics. Studies performed at SU2C Core (Yale and Broad) are part of the the SU2C Lung Cancer Dream Team.

Table 18. Tissue Summary

Order Priority ^a	Tissue Correlative Study	Baseline	C1D11-13	Progression	Slides ^c	Cell Blocks ^b	Institution
1	IHC and QIF of PD-L1 and other Immune Proteins and Tumor Infiltrating Immune Cells	X	X	X	5 minimum (10 ideal)	1	SU2C Immune Core
2	Next Generation Sequencing (tissue + blood for germline DNA comparison)	X		X	20	1	Broad Institute (SU2C Core)
3	RPPA and Multiplex Immunofluorescence for MEK-ERK pathway	X	X	X	4 minimum (10 ideal)	1	[name] Lab UC Davis, Theranostics
5	YAP1/TAZ IHC	X	-	X	2	1	[name] Lab, UCSF

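### The response and PFS analyses of the correlates name no arm term, although markers taken in the lead-in cycle reflect trametinib alone in Arm A and pembrolizumab alone in Arm B

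*Combined protocol and SAP*

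**What the plan says.** Three analyses in Section 8.0 link the correlates to outcome.

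- Response: a descriptive summary "presenting the mean, SD, and other characteristics of molecular and immune measures, stratified by response status".
- If the combination shows activity: "then the correlates will be compared between patients who experience an objective response and those who did not".
- PFS: Kaplan-Meier curves whose stratifying variable is not named and, if numbers permit, "by proportional hazards models with molecular and immune responses as predictors".

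None of these names arm, and the text around them treats the combination as a single entity.

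On the timing of tissue, Section 6.0, footnote 9, states: "Repeat biopsy will be performed on cycle 1 D11-13 or within 2 days after the last dose of trametinib for Arm A". Section 7.1.2.7 gives cycle 1, day 11, plus or minus 2 days. Either window falls within cycle 1. On the drugs given by then, Section 5.2 states for Arm A: "Trametinib will be administered starting C1D1 and pembrolizumab will be added to trametinib starting C2D1"; and for Arm B: "Pembrolizumab will be administered starting C1D1 and trametinib will be added to pembrolizumab starting C2D1".

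Table 18, note a, sends the C1D11-13 biopsy for p-MEK and DUSP6 immunofluorescence and immune IHC/QIF. Section 6.0, footnote 10, and Section 7.1.2.7 also call for plasma DNA/RNA before every cycle, so the draw before cycle 2 follows the lead-in drug alone.

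**The concern.** In the lead-in cycle the same assay on the same day measures a different exposure in each arm. If trametinib and pembrolizumab move a marker differently, arm predicts the marker. If the arms also differ in response rate or PFS, arm predicts the outcome. A responder versus non-responder contrast that ignores arm then contains the drug effect. An inert marker can look predictive, and a real association can be weakened or reversed in appearance. If the outcomes are equal in the two arms there is no bias, but the between-arm marker difference adds to the residual variance and hides a true association.

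The protocol makes this pattern plausible. Section 4.3.1 reports that another MEK inhibitor changed PD-1 on CD8 T-cells and depleted Treg in KRAS mutant NSCLC. Section 3.3 hypothesises that lead-in trametinib will look best on both clinical outcome and immune micro-environment. Arm B has received no MEK inhibitor when p-MEK and DUSP6 are read.

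At stake are the reading of mechanism, the explanation of activity or its absence, and the supplementary evidence for later work on dosing and sequencing.

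**Working it through.** **Inputs from the documents.** Section 8.0 gives 12 patients per expansion arm, a reference response rate of 25% and a target of 50%. Its decision rule (at least 5 of 12) reproduces: exact alpha 0.158, stated as 0.16, and exact power 0.806, stated as 80%. That figure is not in question; it supplies the sample size and response rates used below.

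**Assumptions.** The documents give no marker SD or expected shift. Let d be the Arm A minus Arm B difference in a lead-in-cycle marker, in within-arm SDs, taken as 0.5, 1 and 2. Let b be the true within-arm difference between responders and non-responders. Markers are normal and all 24 patients have usable values.

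**Bias, closed form.** With equal arm sizes and response rates pA and pB, the spurious responder minus non-responder difference is

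d x [pA/(pA + pB) - (1 - pA)/((1 - pA) + (1 - pB))].

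At pA = 0.50 and pB = 0.25: 0.50/0.75 - 0.50/1.25 = 0.667 - 0.400 = 0.267. The spurious difference is 0.267d, that is 0.13, 0.27 and 0.53 SD for d = 0.5, 1 and 2.

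**Variance, closed form.** At equal response rates the bracket is zero, but ignoring arm inflates the SD by the square root of (1 + d²/4): 1.03, 1.12 and 1.41.

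**Simulation.** At least 8,000 trials per setting, two-sided nominal 5% level. A t-test ignoring arm is compared with a linear model containing arm and response.

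| Setting | d = 0.5 | d = 1 | d = 2 | With arm |
|---|---|---|---|---|
| False positives: pA 50%, pB 25%, b = 0 | about 6% | 8-9% | 15% | 5% |
| Power: pA and pB 50%, b = 1.2 SD | about 75% | 69% | 47% | 76% |

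If the arm with the higher marker has the lower response rate (pA 25%, pB 50%) and b = 1 SD, the expected unadjusted difference is 1 - 0.267d, or 0.73 SD at d = 1 and 0.47 SD at d = 2. Power is then about 30% and 10%, against 55% with arm.

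**Which measures are affected.** Setting the sampling schedule against the dosing schedule:

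- Affected: C1D11-13 immune IHC/QIF and p-MEK/DUSP6, changes from baseline based on them, and plasma DNA/RNA before cycle 2.
- Not affected by this mechanism: baseline PD-L1, KRAS substitution and mutational load; sequencing and YAP1/TAZ, which Table 18 places at baseline and progression; immune blood before cycles 4 and 7, by when both arms have been scheduled for both drugs since cycle 2.
- One loose end: the tissue collection text in Section 7.1.2.7 also routes second-biopsy cores to DNA/RNA sequencing. Any expression result from that tissue would join the affected group.

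**Other text that might supply the arm term.** Section 8.0 describes marker levels and changes by sequencing scheme, which is marker by arm, not marker by outcome. Its logistic and proportional hazards regressions estimate arm effects on response and PFS adjusted for clinical covariates, and only if both arms qualify with comparable results. Neither adjusts the marker-outcome association for arm.

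**The case against.** The plan never says that the arms are combined; that is inferred from silence. The separate summaries by sequencing scheme would let a careful reader see a drug-driven shift beside the responder tables. This is fair as to intent. But a table built as written, by response status, mixes the two exposures, and nothing directs the analyst to separate them.

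The associations are described as exploratory and mainly descriptive, with unadjusted p-values and no test named for the responder contrast. The 5% test is therefore a yardstick, not the plan's own claim. That stands, and it limits the priority. It does not remove the bias in the descriptive difference, because the exploratory label addresses multiplicity and imprecision, not a known difference in exposure.

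The size depends on d. At 0.5 SD it is slight, and the large losses belong to d = 2. With only 8 usable pairs per arm the false-positive rate is 7.4% at d = 1 and 11% at d = 2. This stands.

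The strongest objection is to replacing the unadjusted analysis with an adjusted one. If lead-in trametinib works through the marker, as the hypothesis in Section 3.3 allows, conditioning on arm removes real signal. In a simulation where the marker drives response and arm has no direct effect (the strength of that link being assumed), unadjusted against adjusted power was 44% against 35% at d = 1 and 66% against 35% at d = 2. This also stands: neither analysis is sufficient alone.

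**Conclusion.** The point holds for measures taken in the single-drug lead-in cycle and for changes computed from them. For these, the responder contrast and the PFS models as written cannot separate a drug effect from a biomarker association. Bias needs a difference by arm in both marker and outcome; loss of power needs only the marker difference. The size runs from negligible at d = 0.5 to material at d = 2, and rests on assumed shifts, 12 complete pairs per arm and normal markers. The effect on the PFS models follows by the same reasoning but was not calculated.

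Three stronger readings are not supported. A reader might infer that every immune and molecular correlate is compromised; the sampling schedule shows otherwise. A reader might infer that the arm-adjusted analysis is simply the correct one; possible mediation rules that out. A reader might infer that the choice between sequences is undermined; Section 8.0 makes response rate and toxicity the primary considerations, and the correlate inputs to that choice are marker changes per scheme, not the responder contrast. Because the analyses are exploratory and supplementary, the priority is low to moderate.

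**What to change.** In Section 8.0, for lead-in-cycle measures only (C1D11-13 tissue assays, changes from baseline based on them, and plasma DNA/RNA before cycle 2):

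1. Present the summaries by arm and response status.
2. Report a responder contrast from a linear model with arm beside the unadjusted contrast.
3. Report an arm-stratified proportional hazards model beside the unstratified one, and state what stratifies the Kaplan-Meier curves.
4. State that the unadjusted result includes any between-arm drug effect, and that the adjusted result removes any effect of arm that acts through the marker.

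Baseline measures and later blood samples stay as planned.

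The cost is a few sentences of plan text and no new data. The adjusted model spends one degree of freedom. With no marker shift and b = 1 SD, that lowers power from about 63% to 61% at equal response rates, and from about 60% to 55% at 25% against 50%. Cells within 12 patients per arm will be small, so the by-arm summaries are for display rather than inference.

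### The adjusted ORR comparison of the two arms is planned as ordinary logistic regression with four terms in about 24 patients; a penalised fit would be safer, and the result can only be descriptive

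*Combined protocol and SAP*

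**What the plan says.** Section 8.0 (Statistical Analysis Plan) makes the comparison conditional: "If both arms A and B meet the safety criteria and preliminary efficacy criteria and give comparable response rates and toxicities". Regression models are then to account for "key patient differences (PD-L1 status, KRAS amino acid substitution (G12C vs. non-G12C), smoking status". For response, "We will assess whether one arm has superior ORR, using logistic regression analysis to control for clinical covariates". For progression-free survival, the plan will assess "whether one arm has superior PFS, using proportional hazards models to control for clinical covariates".

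On size, "A group of 12 patients will be enrolled in each of the 2 expansion cohorts at the MTD". On the analysis set, "All patients who receive a dose of pembrolizumab and trametinib will be analyzed for safety and efficacy". The section does not say whether dose-escalation patients enter the arm comparison, so 24 is the natural reading but not a stated one.

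It names no penalised or exact method, gives no coding for PD-L1 or smoking, and has no rule for small or empty categories. Its one proviso about sufficient numbers belongs to the models relating biomarkers to PFS, not to these. The regression is followed by a look at biomarkers, and the investigators' judgment then decides.

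**The concern.** With three binary covariates the response model has four slopes and an intercept. If a small category, such as a handful of never-smokers, all respond or all fail to respond, maximum likelihood gives that term no finite estimate (separation). Software then stops or prints a huge odds ratio with a meaningless Wald interval. Ordinary logistic regression is also biased away from an odds ratio of 1 in small samples, even when every estimate is finite.

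This model runs exactly when the raw response rates do not distinguish the arms. An exaggerated adjusted odds ratio could then pass for a real difference between sequences. If the fit fails, the analyst must drop a covariate, merge categories or change method after seeing outcomes in an open-label trial whose arms fill one after the other.

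**Working it through.** **The plan's own figure.** A sequence is "promising if at least 5 of 12 patients were to achieve a complete or partial response". With X binomial on 12 patients, P(X ≥ 5) is 0.158 at a 25% response rate and 0.806 at 50%. This matches the stated alpha of 0.16 and power of 80%. The plan gives no operating figure for the arm regression.

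**Information in the model.** If each arm has at least 5 responders, there are at least 10 in total; 10 to 14 is a plausible range. Over four slopes that is 10/4 = 2.5 to 14/4 = 3.5 responders per slope.

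**Simulation set-up.** Each simulated trial had 12 + 12 patients, no true arm effect and three independent binary covariates. Separation was detected by linear programming, with a separate check of whether the arm coefficient diverges. Each setting used 600 to 1,000 trials. The trigger was read as both arms at 5/12 or more and within 2 responders of each other; the second part is an assumed meaning of comparable. Prevalences and covariate effects are assumptions. The documents say only that most tumours are expected to have lower PD-L1 expression.

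**Separation at ORR 50%, trigger applied**

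| PD-L1-high / G12C / smoker (%) | Covariate odds ratios | Some coefficient not finite | Arm coefficient not finite |
|---|---|---|---|
| 50/50/50 | 1/1/1 | 2% | 0.8% |
| 30/50/50 | 1/1/1 | 5% | 0.9% |
| 20/50/50 | 1/1/1 | 16% | 0.5% |
| 10/50/50 | 1/1/1 | 43% | 0.7% |
| 50/40/80 | 1/1/1 | 18% | 0.8% |
| 30/40/80 | 3/1/2 | 31% | 1.2% |
| 30/40/90 | 1/1/1 | 45% | 0.7% |
| 30/40/90 | 3/1.5/3 | 56% | 1.7% |
| 20/40/90 | 5/2/3 | 70% | 1.2% |

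Across repeat runs the arm figure stayed at about 0.3-2%. At 90% smokers, 7-10% of trials also had a covariate with only one category, which must be dropped under any method.

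**Qualifying on PFS.** The efficacy criteria accept a median PFS of 8 months as an alternative to 50% ORR, so response could be lower. At ORR 25%, with arms within 2 responders, some coefficient was not finite in 22-58% of trials. The arm coefficient was not finite in about 6-11% across runs.

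**Pooling escalation patients.** With 36 patients (18 per arm) at ORR 50% and no trigger applied, the full-model figure was 0-50% and the arm figure was under 1%.

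**Inflation of a finite arm effect.** This was measured in non-separated trials with no true difference and raw responses within 2 patients.

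| Setting | Arm odds ratio beyond 3-fold, maximum likelihood | Same, Firth |
|---|---|---|
| ORR 50%, both arms ≥ 5/12 | about 7-10% | about 2-4% |
| ORR 25% | about 15-20% | about 5-7% |

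The average absolute log odds ratio was 22-28% smaller with Firth.

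**Precision after the fix.** At ORR 50% the median standard error of the Firth arm log odds ratio was about 0.93-0.96. The 95% interval runs from the estimate divided by, to the estimate multiplied by, exp(1.96 × 0.93) = 6.2 to exp(1.96 × 0.96) = 6.6. At ORR 25% the standard error was 1.05-1.08, so the factor is exp(1.96 × 1.05) = 7.8 to exp(1.96 × 1.08) = 8.3. For comparison, unadjusted two-sided 5% power for 50% against 75% with 12 per arm is 24%.

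**The case against.** The strongest objection is that separation somewhere in the model is not failure of the arm comparison. If the few non-smokers all respond alike, the smoking term diverges while the arm estimate stays finite. The trigger also removes most of the lopsided data sets in which the arm term could diverge. This stands. A reader might infer from the sample size that the arm comparison will often have no finite estimate, or that the arm odds ratio becomes infinite. The documents do not support either reading: they give no prevalences, and under the trigger the arm term diverged in 2% of trials or fewer at ORR near 50%.

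It is also fair that the regression carries no alpha, threshold or go/no-go rule. Section 8.0 makes ORR and toxicity the primary considerations, treats the models as additional information and leaves the choice to judgment. That lowers the severity.

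A third objection is that imprecision is the main limitation and Firth does not cure it. This is correct, and it is why the descriptive label and the unadjusted interval are needed. It does not answer the inflation, which Firth reduces substantially.

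Finally, a reader might extend the point to the PFS model. No separation or bias was examined there, so no need to change it has been shown.

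**Conclusion.** The point holds as a low-severity improvement. Ordinary logistic regression on arm plus three covariates in about 24 patients leaves some coefficient without a finite estimate in roughly 2% of trials if covariates are balanced. The figure reaches about 70% with few non-smokers, few PD-L1-high patients and strong covariate effects. The arm odds ratio is rarely the term that diverges (about 0.3-2% at ORR near 50%, about 6-11% near 25%).

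The firmer reason to act is inflation. Between arms that do not differ and look alike on raw response, ordinary fitting shows a more than 3-fold adjusted odds ratio about three times as often as Firth does.

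These sizes rest on assumed prevalences and effects, independent binary covariates, 12 patients per arm, and comparable meaning within 2 responders. The ORR 50% results use the 5-of-12 rule as the efficacy criterion. Section 8.0 also states the criterion as ORR of at least 50%, which would need 6 of 12.

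**What to change.** In Section 8.0, where the two-arm comparison is described:

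- Fit the ORR model by Firth penalised likelihood with profile-likelihood intervals.
- Report the unadjusted ORR difference with an exact confidence interval beside it.
- Label the adjusted comparison descriptive, and say that its 95% interval is expected to span roughly 6-fold either way.
- State the coding of PD-L1 and smoking, what happens when a covariate has a very small or single category, and whether escalation patients are included.

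Penalising the Cox model is optional. The cost is a few lines of SAP wording and some shrinkage of the estimated effect towards no difference (22-28% on the log odds scale in the simulations with no true difference). Design, sample size and data collection do not change.
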